## **10 Statistical methods and data analysis**

It is planned that the data from all centers participating in the trial will be combined, so that an adequate number of patients are available for analysis. Novartis and/or a designated CRO will perform all analyses.. Any data analyses performed independently by any investigator should be submitted to Novartis before publication or presentation.

### **10.1 Analysis sets**

#### **10.1.1 Full analysis set**

The FAS comprises all randomized patients. Following the ITT principle, patients will be analyzed according to the treatment and strata they have been assigned to during the randomization procedure.

#### **10.1.2 Safety set**

[figure not shown]
The Safety Set includes all patients who received at least one dose of study medication defined as fulvestrant, or ribociclib/placebo and had at least one post-baseline safety assessment. Patients will be analyzed according to the study treatment they actually received. Actual treatment refers to the treatment that the patient was randomized to, unless the alternative treatment was received throughout the trial. Please note: the statement that a patient had no adverse events (on the Adverse Event eCRF) constitutes a valid safety assessment.

#### **10.1.3 Per-protocol set**

The per-protocol set (PPS) will include the subset of the patients in the FAS without major protocol deviations. All protocol deviations or conditions leading to exclusion from the PPS will be detailed in the data handling plan and analysis plan. Sensitivity analyses of the primary endpoint of PFS may be performed using data from the PPS if the FAS and PPS differ and if the primary analysis is significant.

#### **10.1.4 Pharmacokinetic analysis set**

The PK Analysis Set (PAS) will consist of all patients who receive at least one dose of study treatment (ribociclib/placebo or fulvestrant) and have at least one evaluable post-dose concentration measurement.

### **10.1.5 Cross-over analysis set**

The cross-over analysis set includes all patients in the placebo arm of the Safety set, ongoing at the time of protocol amendment 4, who elected to cross-over to receive LEE011 combination therapy and received at least one dose of LEE011. This population will be used for the analysis of cross-over phase data. The cross-over phase refers to the time from first dose of LEE011 treatment following cross-over until withdrawal from the study or death.

### **10.2 Patient demographics/other baseline characteristics**

Demographic and other baseline data including disease characteristic/prognostic data will be summarized descriptively by treatment group using data from the FAS. Categorical data will be presented as frequencies and percentages. For continuous data, mean, standard deviation, median, 25th and 75th percentiles, minimum, and maximum will be presented.

### **10.3 Treatments (study treatment, concomitant therapies, compliance)**

The safety set will be used for the analyses below.

The actual dose and duration of fulvestrant, and ribociclib/placebo treatment, as well as dose intensity (computed as the ratio of actual dose received to actual duration) and the relative dose intensity (computed as the ratio of the dose intensity to planned dose received/planned duration), will be listed and summarized using descriptive statistics. The total daily doses of fulvestrant and ribociclib/placebo for each patient will be summarized using descriptive statistics (e.g. mean, median, and mode).

[figure not shown]
Concomitant medications and significant non-drug therapies will be listed by patient and summarized by ATC (Anatomical Therapeutic Chemical classification system) term for each treatment group. These summaries will include medications starting on or after the start of study treatment or medications starting prior to the start of study treatment and continuing after the start of study treatment. Any prior concomitant medications or significant non-drug therapies starting and ending prior to the start of study treatment will be listed.

Compliance to the study drug will be assessed by the number of dose reductions and dose interruptions.

The duration of exposure to study treatment and each component of study treatment will also be summarized for the cross-over phase in patients who crossed over to LEE011 combination therapy after unblinding (i.e. using the Cross-over analysis set).

### **10.4 Primary objective**

The primary objective in the study is to determine whether treatment with fulvestrant + ribociclib prolongs PFS compared to treatment with fulvestrant + ribociclib placebo in men and postmenopausal women with HR+, HER2- advanced breast cancer who received no or only 1 line of prior hormonal therapy for advanced breast cancer.

#### 10.4.1 Variable

The primary efficacy endpoint of the study is PFS, defined as the time from the date of randomization to the date of the first documented progression or death due to any cause. If a patient has not had an event, PFS will be censored at the date of the last adequate tumor assessment (see RECIST 1.1 in [Appendix 2](#) for further details). Clinical deterioration without objective radiological evidence will not be considered as documented disease progression. PFS will be assessed via a local radiology assessment according to RECIST 1.1.

#### 10.4.2 Statistical hypothesis, model, and method of analysis

The primary efficacy analysis will be the comparison of PFS between the two treatment groups using a stratified log-rank test at one-sided 2.5% level of significance.

Assuming proportional hazards model for PFS, the following statistical hypotheses will be tested to address the primary efficacy objective:

$H_0: \theta_1 \geq 0$  vs.  $H_a: \theta_1 < 0$

where  $\theta_1$  is the log-hazard ratio (fulvestrant+ribociclib arm vs. fulvestrant + placebo arm) of PFS.

The primary efficacy endpoint PFS will be analyzed at the interim look/analysis and final look of a group sequential design based on the FAS population according to the treatment group patients were randomized to and the strata they were assigned to at randomization (strata formed using the randomization factor as obtained via IRT). PFS will be estimated using the Kaplan-Meier method. The median PFS along with 95% confidence intervals will be presented by treatment group.

#### 10.4.3 Handling of missing values/censoring/discontinuations

PFS will be censored if no PFS event is observed before the cut-off date. The censoring date will be the date of last adequate tumor assessment before cutoff date. If a PFS event is observed after two or more missing or non-adequate tumor assessments, then PFS will be censored at the last adequate tumor assessment. If a PFS event is observed after a single missing or non-adequate tumor assessment, the actual date of event will be used (see RECIST 1.1 [Appendix 2](#)).

#### 10.4.4 Supportive analyses

As a sensitivity analysis, the distribution of PFS will be compared between the treatment groups using an unstratified log-rank test and the hazard ratio along with the associated 95% confidence interval resulting from an unstratified Cox model will be presented.

The primary analysis for PFS may be repeated with data based on PPS if the primary analysis is statistically significant. Other sensitivity analyses may be performed such as (1) including PFS events even if the events are recorded after two or more missed assessments, (2) backdating events occurring after missing tumor assessments.

Subgroup analyses will be performed on each level of stratification factors if the primary analysis is significant. The analysis will include Kaplan-Meier summaries and estimation of hazard ratios from un-stratified Cox regression models. Additional subgroup analyses to assess the homogeneity of treatment effect based on demographic and baseline disease characteristics

may be performed; details about the subgroups to be included will be provided in the study analysis plan.

Patterns of censored data will be examined by the treatment groups using descriptive statistics (the numbers of censored patients and reasons for censoring).

PFS assessed by BIRC will serve as supportive evidence of the primary end point. Two methods will be used to summarize the data from the BIRC assessment. The NCI (National Cancer Institute) method (Dodd et al. 2011), uses an auxiliary variable estimator of the log-hazard ratio that combines information from patient-level investigator assessment from all patients and the BIRC assessment of patients randomly selected for central review. This estimate and its one-sided 95% CI will be provided. Details of the audit sample size calculation for the BIRC assessment are provided in [Section 10.8](#). The NCI method will be used for audit sample size determination and summary of treatment effect (HR, 95% confidence intervals) based on the supportive BIRC assessment.

The data from the BIRC assessment generated following the sampling scheme as above will also be summarized using the method proposed by Amit et al. 2011, referred to as the PhRMA (Pharmaceutical Research and Manufacturers of America) method. With this approach, the DD (differential discordance) of early discrepancy rate (EDR) and late discrepancy rate (LDR) between the two arms will be estimated as the rate on the fulvestrant+ribociclib arm minus the rate on the fulvestrant+placebo arm. The EDR and LDR results will also be summarized by treatment arm.

Since the primary endpoint of PFS was met at the time of the primary analysis, no further formal analyses of PFS are planned.

Note: A descriptive analysis of PFS was performed at the time of second OS interim analysis with the aim to update the PFS median for the first line patients since the median for that patient population was not met in the primary PFS analysis.

If any descriptive analyses of PFS are performed after allowing patients ongoing on study treatment in the placebo arm to cross-over to the LEE011 combination arm (permitted after the study had met its primary and key secondary endpoints), appropriate sensitivity analyses will be considered and described in the SAP, for example censoring PFS at the last adequate tumor assessment prior to cross-over for patients in the cross-over analysis set.

## 10.5 Secondary objectives

The secondary objectives in this study are to compare the two treatment groups with respect to overall survival (OS), and evaluate overall response rate (ORR), clinical benefit rate (CBR), time to response (TOR), duration of response (DOR) and time to definitive deterioration in the quality of life and ECOG PS, safety. OS between the 2 treatment arms will be statistically compared. A hierarchical testing strategy will be taken to control overall type-I error rate; therefore OS will be statistically evaluated and interpreted only if the primary efficacy endpoint PFS is significantly different between the 2 treatment groups.

### 10.5.1 Overall Survival

One of the secondary objectives of the study is to determine whether treatment with fulvestrant + ribociclib prolongs overall survival (OS) compared to treatment with fulvestrant + placebo.

OS is defined as the time from date of randomization to date of death due to any cause. If a patient is not known to have died, then OS will be censored at the date of last known date patient alive.

Assuming proportional hazards model for OS, the following statistical hypothesis for OS will be tested using a stratified log-rank test (stratified according to randomization stratification factors) at the one-sided 2.5% level of significance:

$H_0: \theta_2 \geq 0$  vs.  $H_a: \theta_2 < 0$

where  $\theta_2$  is the log-hazard ratio (fulvestrant+ribociclib arm vs. fulvestrant+placebo arm) of OS.

The analyses for OS will be based on the FAS. The distribution of OS will be compared between the two treatment groups using a stratified log-rank test at one-sided 2.5% level of significance.

[figure not shown]
The final OS analysis will not be performed at the time point of the final PFS analysis, but after additional follow-up. Therefore, a four-look design is considered for OS.

1. OS will be hierarchically tested (provided the primary PFS analysis is statistically significant) in the following way. The first potential time point for OS analysis will be at the time of the primary PFS analysis at which time approximately 161 deaths are expected. If PFS is statistically significant at this stage, OS will also be tested. If OS is not statistically significant at this stage, the 2nd OS analysis is planned after approximately 263 deaths are expected. If OS is not statistically significant at this stage, the final OS analysis will be planned after approximately 351 deaths.

The type I error probability for OS tests will be controlled by using a separate Lan-DeMets (O'Brien-Fleming) alpha spending function independent of the one used for the primary efficacy analysis of PFS at the one-sided type I error of  $\alpha=0.025$ . This guarantees the protection of the overall level  $\alpha = 2.5\%$  across the two hypotheses and the repeated testing of the OS hypotheses in the interim and the final analyses ([Glimm 2010](#)).

The distribution function of OS will be estimated using the Kaplan-Meier method. The median OS along with 95% confidence intervals will be presented by treatment group. The stratified Cox regression will be used to estimate the hazard ratio (HR) of OS, along with 95% confidence interval.

Since the secondary endpoint of OS was met at the second interim analysis, no further formal analyses of OS are planned. If any descriptive analyses of OS are performed after allowing patients ongoing on study treatment in the placebo arm to cross-over to the LEE011 combination arm (permitted after the study met its primary and key secondary endpoints), appropriate sensitivity analyses will be considered and described in the SAP, for example censoring OS at the date of first LEE011 treatment for patients in the crossover analysis set.

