## 6 Treatment

### 6.1 Study treatment

For this study, the term “investigational drug” refers to Novartis study drug ribociclib. Fulvestrant is also being used in this study. Study treatment in this study refers to the combination of drugs in each of the study arms and includes ribociclib/placebo and fulvestrant.

Ribociclib will be supplied by Novartis or its designee as 200 mg hard gelatin capsules as individual patient supply packaged in bottles.

Fulvestrant will be procured locally according to local practice and regulation, or supplied by Novartis (or its designee). Storage conditions are described in the medication label. Medication labels will comply with the legal requirements of each country and be printed in the local language.

All dosages prescribed and dispensed to the patient and all dose changes during the study must be recorded on the Dosage Administration Record eCRF.

The study met its primary efficacy endpoint (PFS) at the time of the primary analysis. It also met the secondary efficacy endpoint of OS at the time of the pre-planned 2nd interim OS analysis.

Given the demonstrated survival benefit, patients and investigators will be unblinded to the treatment allocation. Additionally, patients who remain on study and are currently allocated to the placebo + Fulvestrant arm, will be given the opportunity to transition to the ribociclib + Fulvestrant combination.

Unblinded study treatment period will end once a patient discontinues from the study treatment for any reason or the end of study (EOS) is declared, whichever occurs first.

Following protocol amendment 4 and the unblinding of study participants, the word “placebo” refers to the original treatment allocation in the study. Physical placebo capsules no longer need to be administered but the reference to placebo has been kept in places in the protocol to avoid confusion.

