### **10.7.2 Overall survival (OS)**

OS will be compared between the two treatment groups, provided the primary endpoint PFS is statistically significant favoring the test treatment arm (ribociclib + fulvestrant). A gatekeeping testing procedure will be adopted in this study and the OS analyses will be performed only if the primary efficacy endpoint PFS is statistically significant. A maximum of 3 analyses is planned for OS; at the time of the final analysis for PFS (provided PFS is significant), at which point approximately 161 deaths are expected, after approximately 263 events have been

documented), and a final analysis for OS when approximately 351 deaths are expected (expected 56 months from date of first patient to be randomized).

An  $\alpha$ -spending function according to Lan-DeMets (O'Brien-Fleming) independent of the one used for the primary efficacy analysis, (as implemented in East 6.3) along with the testing strategy outlined below will be used to maintain the overall type I error probability (Lan and DeMets 1983). This guarantees the protection of the 2.5% overall level of significance across the two hypotheses and the repeated testing of the OS hypotheses in the interim and the final analysis (Glimm 2010). The trial allows for the stopping of the study for a superior OS result, provided the primary endpoint PFS has already been shown to be statistically significant favoring the test treatment arm (ribociclib +fulvestrant). Further, the exact nominal p-values that will need to be observed to declare statistical significance at the time of these analyses for OS will depend on the number of OS events that have been observed at the time of these analyses and the  $\alpha$  for OS already spent at the time of earlier analyses.

The projected timing of interim analysis is summarized in Table 10-1.

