### **Power for analysis of overall survival**

OS will be compared between the two treatment arms, provided that the primary endpoint, PFS, is statistically significant. The power statements for overall survival below are therefore conditioned on significant primary PFS result. Estimate of first line median OS with fulvestrant alone is not published. However the median OS with fulvestrant alone in first line setting is expected to be between 34 months (letrozole alone, [Mouridsen 2003](#)) and 38 months (anastrozole alone, FACT trial, [Bergh et al 2012](#)) based on results from endocrine based monotherapy studies. For sample size calculation, we assume the median OS for fulvestrant alone in first line to be 38 month. Median OS for fulvestrant in relapsed post-menopausal advanced breast cancer patients is estimated to be between 19 months (SoFEA trial, [Johnston et al 2013](#)) and 26 months (CONFIRM trial, [Di Leo et al 2014](#)). For sample size calculation, the mOS for fulvestrant in second line is assumed to be 26 months. Based on the expected split of first line and second line patients mentioned above, the median overall survival of control arm is estimated via simulation to be approximately 30 months. It is hypothesized that adding ribociclib to fulvestrant will result in a 29% reduction in the hazard rate for OS (corresponding to an increase in median survival to 42 months). To detect a hazard ratio of 0.71 with 85% cumulative power, a maximum of 353 deaths need to be observed, (using a log-rank test and a 3-look [superiority only] group sequential design at one-sided cumulative 2.5% level of significance). The sample size calculation was conducted with software package East 6.3.

Based on the number of patients planned to be randomized and 10% dropout rate by the time of OS final analysis, it is estimated that these 353 deaths will be observed at approximately 56 months after the randomization of the first patient. Therefore the estimated time for the final OS evaluation will be 30 months after the primary analysis of the PFS endpoint.

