3.8.2.1 Overall survival

Comparing the overall survival (OS) between ribociclib +fulvestrant and placebo+fulvestrant is a secondary objective in this study. OS is defined as the time from date of randomization to date of death due to any cause. If a patient is not known to have died at the time of analysis

cut-off, then OS will be censored at the date of last contact. Assuming proportional hazards for OS, the following statistical hypotheses will be tested:

$$H_{02}: \theta_2 \geq 0 \text{ vs. } H_{A2}: \theta_2 < 0$$

Where θ_2 is the log OS hazard ratio (fulvestrant+ ribociclib arm vs. fulvestrant + placebo arm). The analysis to test this hypothesis is a stratified log-rank test at an overall one-sided 2.5% level of significance. The stratification will be based on the randomization stratification factors.

A maximum of 3 analyses are planned for OS: at the time of the analysis for PFS (provided PFS is significant), at which point a total 161 deaths (46% of OS events) are expected, after 263 events (75% of OS events) have been documented, and a final analysis for OS when 351 deaths (100% of OS events) are expected (expected 56 months from date of first patient to be randomized).

OS tests will be carried out using a Lan-Demets (O'Brien-Fleming) alpha spending function. OS will only be tested if the primary efficacy analysis has been shown to be statistically significant. Analyses will be based on the FAS population according to the randomized treatment group and strata assigned at randomization. All deaths recorded up to the cut-off date will be included in the analysis. The survival distribution of OS will be estimated using the Kaplan-Meier method, and Kaplan-Meier curves, medians and 95% confidence intervals of the medians intervals along with the proportion of patients alive at 6 month interval starting from 12 month will be presented for each treatment group. The hazard ratio for OS will be calculated, along with its 95% confidence interval, using a stratified Cox model using the same stratification factors as the log-rank test.

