4.2.2 Hazard ratio

The hazard ratio as a measure of treatment effect will be derived from the Cox proportional hazards model using SAS procedure PHREG with TIES=EXACT option in the MODEL statement. The stratified unadjusted Cox model will be used (where the baseline hazard function is allowed to vary across strata) for the primary analysis, i.e. the MODEL statement will include only the treatment arm variable as a covariate and the STRATA statement will include stratification variable(s).

Hazard ratio with two-sided 95% confidence interval will be based on Wald test.

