4.3.1 Alpha-spending function

The stopping boundaries to be used for OS test will be calculated using the α -spending function approach described in Lan and DeMets ([Lan and DeMets, 1983](#)). The spending function for one-sided test has the following functional form:

$$\alpha(t) = 2 - 2\Phi(Z_{\alpha/2} / \sqrt{t})$$

This function generates stopping boundaries that closely resemble the O'Brien-Fleming boundaries (O'Brien and Fleming, 1979).

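### OS is tested against O'Brien-Fleming boundaries, but the only planned OS interval is an unlabelled ordinary 95% Cox interval, which can exclude 1 at an interim look where OS is not significant

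*Protocol*

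**What the plan says.** **Test.** Protocol 10.5.1 and 10.7.2 use a Lan-DeMets (O'Brien-Fleming) spending function for OS, and the power section describes the design as "using a log-rank test and a 3-look [superiority only] group sequential design at one-sided cumulative 2.5% level of significance". SAP 4.3.1 gives the spending formula and notes: "This function generates stopping boundaries that closely resemble the O'Brien-Fleming boundaries". Under protocol 10.7.2 and SAP 3.14.2, the nominal p-value needed at each look depends on the deaths observed and the alpha already spent.

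**Number of looks.** Protocol 10.7.2: "A maximum of 3 analyses is planned for OS". Protocol 10.5.1 also says "Therefore, a four-look design is considered for OS", but it then lists three: about 161, 263 and 351 deaths.

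**Reported effect.** Protocol 10.5.1: "The stratified Cox regression will be used to estimate the hazard ratio (HR) of OS, along with 95% confidence interval". SAP 3.8.2.1: "The hazard ratio for OS will be calculated, along with its 95% confidence interval, using a stratified Cox model". SAP 4.2.2: "Hazard ratio with two-sided 95% confidence interval will be based on Wald test". SAP 2.2 refers all of the up to three OS analyses to section 3.8, so this one method serves each of them. SAP 4.3 adjusts the critical values for the interim looks and does not mention the interval.

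**Outcome.** Protocol 6.1: "It also met the secondary efficacy endpoint of OS at the time of the pre-planned 2nd interim OS analysis". Protocol 10.5.1 plans no further formal OS analysis.

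**The concern.** The test and the interval work to different error rates. The test at an interim look demands much stronger evidence than a one-sided p of 0.025, while the interval uses the fixed-sample multiplier of 1.96 throughout. A result can therefore miss the boundary and still carry a 95% interval wholly below 1.

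The first OS look coincides with the primary PFS analysis, and the SAP for that clinical study report contains the OS method. An OS interval below 1, placed beside a positive PFS result and without a label, can be read as a survival finding that the plan's own rule does not accept.

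**Working it through.** **Inputs.** One-sided alpha is 0.025 over three looks (protocol, OS power section). Looks fall at 161, 263 and 351 deaths (protocol Table 10-1). The design HR is 0.71 and allocation is 2:1. Spending is alpha(t) = 2 - 2*Phi(z/sqrt(t)), where z = 2.2414 is the upper 1.25% normal point (SAP 4.3.1). With 2:1 allocation, SE(log HR) = 1/sqrt(2D/9).

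**Reproducing the plan.** Information fractions of 161/351 = 0.459, 263/351 = 0.749 and 1 give cumulative alpha of 0.00093, 0.0096 and 0.025. Numerical integration then gives cumulative power at HR 0.71 of 14.4%, 60.7% and 85.0%. Protocol Table 10-1 and SAP Table 3-9 state 14%, 60% and 85%, so this is the plan's own design.

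**Where test and interval part.** OS is significant when HR < exp(-c*SE). The ordinary 95% interval lies below 1 when HR < exp(-1.96*SE).

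| Deaths | SE | Boundary c | One-sided p needed | HR at boundary | HR below which 95% CI excludes 1 |
|---|---|---|---|---|---|
| 161 | 0.1672 | 3.110 | 0.00094 | 0.595 | 0.721 |
| 263 | 0.1308 | 2.353 | 0.0093 | 0.735 | 0.774 |
| 351 | 0.1132 | 2.013 | 0.0221 | 0.796 | 0.801 |

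The conflict zone is the gap between the last two columns. Two examples:

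- Look 1, observed HR 0.65: 95% CI 0.47 to 0.90, one-sided p 0.0050, not significant.
- Look 2, observed HR 0.76: 95% CI 0.588 to 0.982, one-sided p 0.018, not significant.

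**How often.** At look 1 with true HR 0.71, the mean of Z is 0.3425/0.1672 = 2.049. The conflict probability is Phi(3.110 - 2.049) - Phi(1.960 - 2.049) = 0.856 - 0.465 = 0.391. Simulation of 4 million trials that stop on crossing gives:

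| True HR | Look 1 | Look 2 | Look 3 | Any look |
|---|---|---|---|---|
| 0.71 | 39.1% | 13.9% | 1.1% | 49.2% |
| 1.00 | 2.4% | 1.6% | 0.3% | 3.7% |

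The looks overlap, so they do not add up to the last column. Under no effect, some reported interval lies wholly below 1 in 5.0% of trials, against 2.5% for the test.

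**Behaviour of the interval.** Over true HRs from 0.65 to 1.0, unconditional coverage of the ordinary interval is 93.8% to 95.0%. Given a look-1 crossing at HR 0.71 it is 83%. Given a look-2 crossing at HR 0.85 it is 86%.

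**Effect of matching the boundary.** Replacing 1.96 by c gives levels 2*Phi(c) - 1 of 99.81%, 98.14% and 95.59%. Coverage at stopping becomes 95.3% to 97.8% over the same HRs. The two conditional figures rise from 83% to 99% and from 86% to 96%. In the examples above, the upper limits become 1.09 and 1.03, in line with the test. At look 2 with an observed HR of 0.72, which crosses, the ordinary interval is 0.557 to 0.930 and the matched one 0.529 to 0.980.

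**Sensitivity.** The documents give the final number of deaths as 351, 353 (protocol OS power section) and 361 (text of SAP 3.14.2). Using 353 or 361 moves the boundary HRs by at most 0.005.

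**The case against.** The decision rule does not use the interval. OS is declared by stratified log-rank test against boundaries recomputed from the spending function, and no passage lets a 95% interval below 1 support a claim. A reader might infer from the 5.0% figure that OS type I error is inflated. It is not: the formal test keeps 2.5%, and 5.0% describes only what the printed intervals would show. As an interval procedure, the Cox interval is close to nominal unconditionally. All of this stands, and it limits the point to reporting.

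A reader might also infer that the OS effect reported after the early stop is exaggerated. On average, estimates at a crossing are: with true HR 0.71, the geometric mean is 0.546 at look 1 and 0.670 at look 2. That is an average over trials that cross, not a finding about this trial, and over all stopping points the mean is 0.691. A stage-wise median-unbiased HR would correct little. At a look-1 stop it equals the Cox HR. At look 2 it moves an observed 0.72 to 0.721, and the average from 0.670 to 0.677. It is not worth asking for.

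Three further limits hold. Investigators and patients stay blinded at the first OS look (protocol 10.7.2, SAP 3.14.3). That the first-look interval enters the primary report is an inference from the scope of that SAP; no text describes it as a survival claim. And SAP 3.8.2.1 has a redacted block, so the absence of an adjusted interval can be stated only for the visible text.

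**Conclusion.** The point holds as a mismatch in reporting between the interim OS test and the interim OS interval. At the design HR it is large at 161 deaths (39%), moderate at 263 (14%) and negligible at 351 (about 1%). Because OS crossed the stricter boundary at the second look, test and interval should agree there, and only the first-look report could have shown the conflict. The documents do not give the first-look HR, so they do not show that it did. Nor do they give grounds to doubt the OS significance claim.

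The figures assume the planned death counts, proportional hazards, the normal approximation with information 2D/9, and stopping on crossing. This is a cheap improvement, not a defect in the OS test.

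**What to change.** In protocol 10.5.1 and SAP 3.8.2.1 and 4.3, state that each OS look reports the stratified Cox HR with the repeated confidence interval matched to the boundary used. The levels are about 99.8%, 98.1% and 95.6% at 161, 263 and 351 deaths, recomputed from the actual deaths. Keep the ordinary 95% Cox interval beside it, labelled *not adjusted for interim looks*. The matched interval then agrees with the decision rule, apart from the small difference between the Wald and log-rank statistics.

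The cost is one extra table line and a wider interval; no new data are needed. Formal OS testing is over, so for this trial the change bears on how the OS intervals already obtained are labelled.
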